##### **Gender-related Variables**

1. Food insecurity
2. Self-efficacy

- 3. Perceived decision making
- 4. Perceived social support
- 5. Perceived parental stress

#### 9.4.1 ADDRESSING THE PRIMARY OBJECTIVES

This study has two primary objectives: 1) To assess if alterations of the microbiota in the maternal gut (dysbiosis) are associated with maternal gestational weight gain; and 2) To determine the association between maternal microbiome dysbiosis during pregnancy and birth outcomes, infant growth, nutritional status and health status in the first year of life.

The first objective will be addressed through the following approaches. First, maternal gut bacteria and eukaryotic profiles will be used to calculate Bray-Curtis dissimilarity metrics between individual samples which will be leveraged in principal co-ordinate analyses to determine the extent samples collected at the first or third trimester, exhibiting similar gestational weight gains, co-cluster. Permutational multivariate analysis of variance (PERMANOVA) tests will assess the degree of overlap between samples exhibiting low gestational weight gain versus samples exhibiting high gestational weight gain. A lack of clustering in the first trimester, followed by clustering of samples on the basis of similar gestational weight gain would indicate that alterations in the maternal microbiota during the course of pregnancy, impacts gestational weight gain. Next, we will attempt to correlate changes in the alpha diversity (as measured by the Shannon and Simpson indices) of the gut microbiome samples between the first and third trimester, with gestational weight gain. A decrease in alpha diversity (indicative of dysbiosis) associated with low gestational weight gain, would again indicate that dysbiosis is associated with maternal weight gain. To examine the influence of individual taxa on gestational weight gain, we will perform bivariate analyses that examine the correlation (Pearson, Spearman) of each taxon with gestational weight gain. Correlations will examine taxon abundance in first and third trimester, in addition to the change in abundance between the two trimesters. The Benjamini-Hochberg procedure will be applied to correct p-values while controlling for false-discovery rates.

To complement these analyses, we will also undertake an integrative modeling strategy based on Similarity Network Fusion framework[112] to analyze the contribution of each variable (clinical, microbiome and gender-related) on gestational weight gain. In this approach we construct a series of networks (one for each variable) in which nodes represent patients and links represent similarities between patients (e.g. based on correlations between e.g. microbiome or metabolite profiles). Networks are then fused using a method based on message-passing theory to identify links shared between patients supported by multiple datatypes, eliminating poorly supported links and strengthening links supported by multiple datatypes. This allows the integration of all available datasets to uncover their global substructures that can be associated with gestational weight gain. In an alternative approach, we will also employ Random Forests to identify

combinations of variables (clinical, microbiome and gender-based; Table 8) that correlate with gestational weight gain.

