### 3 STUDY OBJECTIVES

**Table 4: Study Objectives**

OBJECTIVES	ENDPOINTS	JUSTIFICATION FOR ENDPOINTS
Primary		
To assess if alterations of the microbiota in the maternal gut (dysbiosis) is associated with maternal gestational weight gain.	The primary endpoint will be maternal gestational weight gain (GWG) during pregnancy, measured between the first (10-14 weeks post-conception) and second time point (30-34 weeks post conception).  To monitor microbiome dynamics, 16S and 18S rDNA surveys will be	Weight gain is a key predictor of adverse birth outcomes[83, 84].

OBJECTIVES	ENDPOINTS	JUSTIFICATION FOR ENDPOINTS
	
applied to the maternal stool samples to monitor the bacterial and eukaryotic components of the microbiome.
	
To determine the association between maternal microbiome dysbiosis during pregnancy and birth outcomes, infant growth, nutritional status and health status in the first year of life.	
The specific birth outcomes evaluated will include preterm birth, birth weight, SGA, LGA, head circumference at birth, mortality, morbidity.
 
The specific infant outcomes evaluated will include the following growth and nutritional status parameters; WHO z-scores for weight, length, head circumference and MUAC during the first year.
 
Birth characteristics will be collected, including information on vaginal or cesarean birth (elective, emergency), placental insufficiency and antibiotic usage.
 
Infant morbidity and mortality will be assessed at follow-up visits, with questions regarding care-seeking, hospitalizations and treatments for any morbidity; including antibiotic usage.
 
For the infants an assessment of amount and mode of feeding will be obtained at 3-months, 6-months and 12-months.
 
To monitor microbiome dynamics, 16S and 18S rDNA surveys will be applied to the maternal stool samples to monitor the bacterial and eukaryotic components of the microbiome.
	
This will allow for an examination of the association between the maternal microbiome and birth outcomes.

Secondary		
To link the maternal microbiome to dietary intake, with a focus on calories and macronutrients.	
The maternal participants will complete a 24 hour dietary recall at both time points during pregnancy and at 1-year post-partum.
	
Quantitative measures of nutritional status will provide parameters to better inform microbiome analyses.

OBJECTIVES	ENDPOINTS	JUSTIFICATION FOR ENDPOINTS

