## 9 STATISTICAL CONSIDERATIONS

### 9.1 POWER CALCULATION

The adequacy of the sample size was verified using the ‘pwr’ package (version 1.2-2) in R (version 3.6.1). Calculations were based on the correlation between  $\alpha$ -diversity (Shannon index) and weight gain during pregnancy. Assuming 400 participants are recruited into the study, and a type I error rate of 0.05, there will be 80% power to detect a correlation coefficient ( $r$ )  $>0.14$ . This is conventionally considered a small effect size[109]. Thus, we expect to be powered to reveal significant association between weight gain during pregnancy and diversity. Further, a study of 123 lean and 24 obese individuals, revealed 96% power to detect differences in Bacteroidetes abundance and 80% power for Firmicutes[110], while a cohort of 44 Malawian malnourished children was sufficient to detect significant differences in bacterial  $\alpha$ -diversity in the presence and absence of *Blastocystis*.

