##### **Clinical Variables**

1. Maternal BMI, MUAC and SFT (continuous variables)
2. Maternal gestational weight gain (continuous)
3. Maternal markers of inflammation (continuous)
4. Infant sex
5. Infant morbidity and mortality
6. Infant weight, height, head circumference (continuous)
7. Infant gestational age
8. Infant birth weight, Kg (continuous)
9. Breastfeeding duration (continuous)
10. Maternal age years
11. Maternal use of antibiotics
12. Infant use of antibiotics
13. Maternal calorie and macronutrient intake
14. Maternal incidence of pathobionts
15. Infant incidence of pathobionts

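### Section 9.4.1 groups a continuous primary endpoint into low and high weight gain for its PERMANOVA, which costs that test about a fifth to over a third of its information

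*Protocol*

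**What the plan says.** Table 4 in section 3 states: "The primary endpoint will be maternal gestational weight gain (GWG) during pregnancy", measured between the first and second visits. Table 8 in section 9.4 lists "Maternal gestational weight gain (continuous") among the clinical variables.

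Section 9.4.1 gives several approaches to the first primary objective. The first is a Bray-Curtis ordination with PERMANOVA, whose "tests will assess the degree of overlap between samples exhibiting low gestational weight gain versus samples exhibiting high gestational weight gain". No threshold, quantile or group size is given. The section then says how the result will be read: if samples do not cluster in the first trimester but later cluster by similar GWG, this is taken to show that changes in the microbiota during pregnancy affect weight gain.

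The next approaches in the section correlate GWG with the change in alpha diversity and with each taxon, without grouping it. Section 9.4.2 runs PERMANOVA against the clinical variables, a list that includes continuous GWG, but for the secondary objectives. The power statement in section 9.1 also rests on a correlation with weight gain.

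**The concern.** Splitting a continuous variable into two groups treats all women within a group as alike. If the middle of the cohort is dropped to sharpen the contrast, those women's data are lost to the test. PERMANOVA does not need groups: it partitions the distance matrix on a continuous regressor equally well. The protocol therefore gives up information on its primary endpoint for no technical reason, and in only one of the approaches in this section that test GWG directly.

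Two things are at stake. One is the power of this test. The other is the conclusion that the protocol attaches to it. Because a null result at MV1 followed by a positive result at MV2 is read as evidence of impact, a missed association at MV1 counts in favour of the hypothesis. Lower power can then produce the pattern when nothing has changed between the visits.

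**Working it through.** **Inputs.** From section 9.1: "Assuming 400 participants are recruited into the study", "a type I error rate of 0.05", and "there will be 80% power to detect a correlation coefficient" above 0.14. The documents do not state sidedness; two-sided is assumed. Also assumed: GWG is roughly normal and its association with the community axis is linear.

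**Step 1: the protocol's own figure.** Fisher-z power is Φ(atanh(r)·√(n − 3) − 1.960). With r = 0.14 and n = 400: atanh(0.14) = 0.1409, √397 = 19.92, product 2.808, less 1.960 is 0.848, and Φ(0.848) = 80.2%. With the small bias correction used by the R package it is 80.3%. A one-sided test would give 87.8%, so two-sided fits. The stated 80% reproduces.

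**Step 2: efficiency of grouping a normal variable.** With φ the normal density and z_p the normal quantile at p:
- single cut at share p: φ(z_p)² / [p(1 − p)]
- lowest share p against highest share p, middle dropped: 2·φ(z_p)² / p

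The grouped test has a signal of √efficiency × 2.808, and power is Φ(signal − 1.960).

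| Use of GWG | Efficiency | Information lost | Effective n | Power at r = 0.14 |
|---|---|---|---|---|
| Continuous | 1 | 0% | 400 | 80% |
| Outer quarters | 0.808 | 19% | 323 | 71% |
| Outer thirds | 0.793 | 21% | 317 | 71% |
| Median split | 2/π = 0.637 | 36% | 255 | 61% |
| Single cut at one third | 0.595 | 40.5% | 238 | 58% |
| Single cut at 20% | 0.490 | 51% | 196 | 50% |

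Worked example, median split: √0.637 = 0.798; 0.798 × 2.808 = 2.240; 2.240 − 1.960 = 0.280; Φ(0.280) = 61%.

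**Step 3: checks by simulation.** In 10,000 simulated datasets (t-test against correlation), power was 80.5% continuous, 61.3% median split, 70.2% outer thirds, 71.1% outer quarters and 50.3% for a cut at 20%. In a simulated Bray-Curtis PERMANOVA (n = 400, 400 replicates), power was 82% continuous, 59% median split, 70.5% outer thirds and 71% outer quarters. The taxon effects in that second simulation are invented, so it shows only that the relative loss carries over to PERMANOVA.

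**Step 4: effect on the planned reading.** Suppose the same r = 0.14 association exists at both visits, so nothing has changed. If the two tests were independent, the chance of a non-significant MV1 and a significant MV2 is (1 − power) × power:
- continuous: 0.20 × 0.80 = 16%
- outer thirds or quarters: 0.29 × 0.71 = 21%
- median split: 0.39 × 0.61 = 24%

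If the two test statistics correlate at 0.5 (an assumed value), a bivariate normal calculation gives 11%, 14% and 16%. This product peaks at 50% power, so the increase holds for effects that the continuous test would detect with reasonable power, not for very weak ones.

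**The case against.** The strongest reply is that the study's power does not rest on this test. Section 9.1 is explicit: "Calculations were based on the correlation between" Shannon diversity and weight gain. That correlation and the taxon correlations do not group GWG. Section 9.4.1 names no single primary test, and PERMANOVA coming first is only an order of listing. A reader might infer that the first primary objective as a whole is underpowered; the documents do not support that. The r = 0.14 is borrowed from the alpha-diversity calculation, and the absolute power of a PERMANOVA cannot be derived from anything in the protocol. All of this stands, and it limits the point to one analysis and its reading.

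It can also be said that section 9.4.2 already plans a PERMANOVA on clinical variables that include continuous GWG. That is true, and it shows that the better analysis is within the team's plan. But it belongs to the secondary objectives and does not replace the low/high wording for the primary one.

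Two stronger readings should be set aside. A reader might infer that the cut-point will be picked after seeing the data. The protocol gives none for this test, and the rule in section 8.1.4 (100 highest and 100 lowest) covers stool markers and metabolomics only. But a statistical analysis plan may define the groups, so the missing cut-point is not a defect in itself. A reader might also infer from the word overlap that a p-value alone will be reported as clustering. The same section pairs PERMANOVA with an ordination in which separation can be seen, and nothing says that R² will be left out.

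**Conclusion.** The point holds in a limited form. The protocol itself fixes a low/high comparison for a continuous primary endpoint, so an analysis plan that only added a cut-point would still lose information. The loss is about 19% to 21% for outer quarters or thirds, 36% for a median split, and 40% to 51% for single cuts at one third down to 20%. On one axis at r = 0.14 and n = 400, this takes power from 80% to about 70-71%, 61% and 50-58% respectively.

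These figures assume roughly normal GWG, a linear association and all 400 women contributing. They illustrate relative loss and do not give the power of the planned PERMANOVA. The test remains valid; it is less efficient than it need be. What lifts the point above a matter of taste is that section 9.4.1 uses a null result in the first trimester as part of its evidence. The change is worth making, but the study does not stand or fall on it.

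**What to change.** In section 9.4.1, replace the low-versus-high comparison with PERMANOVA run at MV1 and at MV2 with GWG as a continuous term. Report R² with its permutation p-value at each visit, and keep a low/high split only for displaying the ordination. This takes one sentence, uses the same software, and needs no new data or samples.

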To explore the role of the maternal gut microbiome during pregnancy and to identify gut community dynamics in pregnant women and how this impacts differences between dietary intake and nutritional status.	To gain more mechanistic insights into the relationship between microbiome function and maternal health and birth outcomes, metatranscriptomics, metabolomics and markers of inflammation will be selectively deployed on the stool samples.	The output of these analyses are concentrations of metabolites that are expected to correlate with pathway expression data; linked to readouts of microbial gene expression detailing biochemical activity and the taxa responsible.
To investigate socio-economic factors; including gender, poverty, exclusion and empowerment, and their influence on the health of a mother's microbiome (assessed by alpha and/or beta diversity, and absence of pathogens).	Participants will answer questionnaires at two time points: baseline and 3-months post-partum. The questionnaire will assess gender related variables focused on five main metrics: perceived maternal self-efficacy, perceived social support, decision making, perceived stress in addition to socio-economic factors, including food and housing insecurity, and demographic data.	The use of previously validated questionnaires within this population, will allow for comparison between the Pakistan and Toronto cohorts, to account for gender related variables that impact maternal and infant gut health.
To explore the role of the human microbiota on nutritional status by performing fecal microbiota transplants in germ free mice and sterile piglets.	The pregnancy rates, birth outcomes, microbiome dynamics, health outcomes, host nutritional status, inflammation and barrier integrity will be collected and assessed.	Exploiting animal models will allow us to define causal interactions between diet, microbiome, pathogen exposure and nutritional status during pregnancy. Through recapitulating patient phenotypes with fecal microbiome transplants, our animal studies will set the stage for developing new therapeutic strategies that promote gut health.

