#### 9.4.3 ADDRESSING THE EXPLORATORY OBJECTIVES

This study has the following exploratory objectives: 1) To explore the role of the maternal gut microbiome during pregnancy and to identify gut community dynamics in pregnant women and how this impacts differences between dietary intake and nutritional status; 2) To investigate socio-economic factors; including gender, poverty, exclusion and empowerment, and their influence on the health of a mother's microbiome (assessed by alpha and/or beta diversity, and absence of pathogens); 3) To explore the role of the human microbiota on nutritional status by performing fecal microbiota transplants in germ free mice and sterile piglets.

For the first exploratory objective, we will apply the same statistical framework as we utilized for the secondary objectives here, however, we are concerned with changes in the microbiome within a patient from the first to third trimester. Consequently, microbiome structural and functional profiles will be generated from the difference in: 1) taxonomic abundances; 2) gene expression; and 3) metabolite concentrations, between the first and third trimesters. Profile differences will then be utilized in the PERMANOVA and DESeq2 approaches as described above to identify associations between clinical variables and changes in microbiome structure and function.

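### Clustering by weight gain that is absent early and present late is read as a microbiota change that affects the gain, but the contrast tests neither change nor direction

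*Protocol*

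**What the plan says.** Primary objective 1 asks whether dysbiosis is associated with GWG. The Section 3 objectives table defines GWG as the gain between the first visit (MV1, 10-14 weeks) and the second (MV2, 30-34 weeks).

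Section 9.4.1 begins with Bray-Curtis distances and ordination of samples from the first or third trimester. It then applies PERMANOVA to "samples exhibiting low gestational weight gain versus samples exhibiting high gestational weight gain". An interpretive rule comes next. Its premise reads: "A lack of clustering in the first trimester, followed by clustering of samples on the basis of similar gestational weight gain would indicate". The conclusion drawn from that premise is worded causally: "alterations in the maternal microbiota during the course of pregnancy, impacts gestational weight gain".

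Other parts of the plan bear on the point:

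- Section 9.4.1 also correlates the change in Shannon and Simpson indices with GWG. A fall in diversity accompanying low gain "would again indicate that dysbiosis is associated with maternal weight gain".
- For single taxa, Section 9.4.1 says: "Correlations will examine taxon abundance in first and third trimester, in addition to the change in abundance between the two trimesters".
- Section 9.4.3 forms first-to-third-trimester difference profiles for exploratory objective 1 and relates them to the clinical variables: "Profile differences will then be utilized in the PERMANOVA and DESeq2 approaches as described above to identify associations between clinical variables". GWG is item 2 of the clinical variables in Table 8, so it is covered there.
- The Section 3 objectives table gives causal questions to the animal work: "Exploiting animal models will allow us to define causal interactions".

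**The concern.** The rule has three faults.

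1. **It does not test change.** A non-significant result at one visit and a significant one at the next does not show that the two results differ. The approach names no visit-by-GWG term and no within-woman change. For primary objective 1 the plan tests change in alpha diversity and in single taxa, but not in the community. The community-level change test sits under an exploratory objective.
2. **It cannot give direction.** The second stool is collected at about the end of the interval over which GWG accrues. Late clustering could come from microbiota affecting gain, from gain or diet affecting microbiota, or from a shared cause. A first-trimester community that predicts later gain is the temporally ordered evidence, yet it would fail this pattern.
3. **The verb is too strong.** The objective is associational and the study is observational.

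If community structure relates to GWG equally at both visits, chance alone can produce the pattern. Following the rule, the study would then report, for a primary objective, that a change during pregnancy affects weight gain, when the data show neither a change nor a direction.

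**Working it through.** **1. The protocol's own power figure.** Section 9.1 gives N = 400, type I error 0.05, 80% power and r > 0.14. Sidedness is not stated, so two-sided is taken.

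r = tanh[(1.960 + 0.842)/√(400 − 3)] = tanh(0.1406) = 0.1397.

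The formula of the cited R package gives r = 0.1395 for 80% power, and 80.3% power at r = 0.14. The figure reproduces. It covers a correlation between the Shannon index and weight gain, not the PERMANOVA, so per-visit PERMANOVA power has to be assumed and shown as a range.

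**2. How often the pattern arises when nothing changes.** Assumptions: clustering is judged at two-sided p<0.05, and the true association is the same at both visits. Let Z1 and Z2 be bivariate normal test statistics with equal means and correlation ρ. The pattern has probability P(|Z1| < 1.96 and |Z2| > 1.96). At ρ = 0 this is (1 − power) × power, for example 0.5 × 0.5 = 0.25 and 0.2 × 0.8 = 0.16.

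| Per-visit power | ρ=0 | 0.3 | 0.5 | 0.7 | 0.9 |
|---|---|---|---|---|---|
| 20% | 0.160 | 0.134 | 0.113 | 0.088 | 0.050 |
| 50% | 0.250 | 0.202 | 0.167 | 0.127 | 0.072 |
| 80% | 0.160 | 0.134 | 0.113 | 0.087 | 0.050 |
| 90% | 0.090 | 0.078 | 0.068 | 0.053 | 0.031 |
| 95% | 0.047 | 0.043 | 0.038 | 0.030 | 0.018 |
| 99% | 0.010 | 0.009 | 0.009 | 0.007 | 0.005 |
| No association | 0.047 | 0.045 | 0.041 | 0.033 | 0.020 |

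Over 20% to 95% power and ρ from 0 to 0.9, the range is 2% to 25%.

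**3. Simulation of the two-group comparison.** Assumed settings: 400 women, GWG split at the median, 60 log-normal taxa of which 6 relate to GWG equally at both visits, Bray-Curtis PERMANOVA at each visit, 199 permutations, 600 runs per setting. Monte Carlo standard errors are about 0.008 to 0.02.

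| Within-woman correlation | Mean per-visit power | Pattern |
|---|---|---|
| 0.3 | 20%, 46%, 77%, 95% | 0.150, 0.222, 0.138, 0.050 |
| 0.7 | 23%, 49%, 79%, 94% | 0.107, 0.175, 0.115, 0.035 |
| 0.3 and 0.7, no effect | – | 0.043 and 0.045 |

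A direct change test on the same data (PERMANOVA on the Euclidean distance of centred log-ratio change, one possible choice) rejected in 0.033 to 0.065 over all ten settings, close to its nominal 5%. A smaller simulation with other settings (50 against 50 women, 30 taxa, 200 runs) gave the pattern in 24% at about 45% to 54% power, 13% at about 80% and 1% at 99%.

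**4. Timing.** GWG runs from MV1 to MV2 (Section 3). Section 7.1.1.2 has the stool kit handed out at MV2 and a collection day arranged; Section 7.2.1.2 has samples requested before visits. Either way the second sample falls at about the end of the gain interval. It does not precede the outcome that it is said to affect.

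**The case against.** **Separate models per visit are inferred.** The PERMANOVA sentence does not say that each trimester is modelled separately, and model detail can be left to a statistical analysis plan, which is not at hand. This has little force. The rule needs one result for the first trimester and another for later, and the rule itself is fixed in the protocol.

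**The threshold is imported.** Section 9.4.1 describes clustering and overlap as matters of degree and gives no p-value cut-off. This stands as a limit on the size. The error rates depend on p<0.05 and on assumed power and correlation.

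**The error concerns timing, not existence.** With no association at either visit, the pattern arises in 2% to 5% of studies, at or below nominal. This stands. The excess appears only when microbiota and GWG really are related, and what is then wrong is the claim that the relation arose during pregnancy.

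**Change is tested elsewhere.** Alpha diversity and single taxa are tested for change under the same objective, and Section 9.4.3 tests it for the community. This stands and narrows the point to one sentence in one of several approaches. The community-level conclusion for the primary objective still rests on the invalid contrast.

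**The verb may be loose wording.** The next criterion speaks of association and uses the word *again*, which suggests that an association was meant throughout. If so, the wording edit matches the authors' intent.

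**The replacement does not settle direction either.** That is true of any change measured over the same interval as GWG, and it is why the wording has to change as well as the test. The plan already examines first-trimester clustering and correlates first-trimester taxa with GWG, and it does not call the absent-then-present pattern necessary. Reporting the MV1 result in its own right is therefore a matter of emphasis.

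**Conclusion.** The concern holds. The stated rule does not test change, cannot identify direction, and draws a causal conclusion that the objective and design do not support.

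The last two faults hold at any power. The size of the first depends on power: 9% to 25% at 20% to 80% per-visit power with test correlation 0 to 0.7, 5% to 9% at 90%, 3% to 5% at 95%, and about 1% at 99%. These figures assume p<0.05 at each visit and an identical true association at both. The protocol gives no PERMANOVA power, so high power cannot be presumed.

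The fault is confined to one interpretive sentence, but that sentence sets a conclusion for a primary objective. It should be fixed.

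**What to change.** In Section 9.4.1, for primary objective 1:

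1. Replace the absent-then-present criterion with one direct community-level test of change against GWG. This can be the within-woman change PERMANOVA already planned in Section 9.4.3, with a distance that accepts signed differences. It can also be a visit-by-GWG interaction that respects the pairing of samples within woman.
2. Report the MV1 community profile against subsequent GWG as the temporally ordered result.
3. Replace the causal verb with wording of association.

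The cost is a little more analysis, including the choice of a distance for change profiles, and a more modest conclusion. No new samples are needed.

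Power can move either way. With an association simulated at MV2 only and a within-woman correlation of 0.3, the change test had 43% power against 75% for the MV2 comparison. At correlation 0.7 it had 93% against 77%. The two tests also used different distances, so these figures mix the effect of the metric with that of the design. The visit-wise comparisons can stay as description, provided that change is not inferred from them.
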